This study will provide rigorous epidemiologic evidence regarding the influence of fetal exposure to HIV and ART on developmental and mental health outcomes from infancy to adolescence, including obtaining a national population-based estimate of HEU burden of developmental and mental health outcomes and strategies for programmatic surveillance and referral.

11. Specific aims and hypotheses

Aim 1: Within a longitudinal cohort of 1000 HEU and 1000 HUU infants enrolled at 6 weeks of age from 5 MCH clinics and followed 6-monthly:

HOPE study protocol

Version 1.3

July 21, 2020

Aim 1a. To compare HEU and HUU infants and children for growth, hearing, and neurodevelopmental outcomes; and determine influence of ART timing/regimen on HEU outcomes. To determine whether fetal HIV/ART exposure impacts 4-year neurodevelopmental outcomes; and assess impact of peripartum ART regimen and timing.

Aim 1b: To compare telomere length in HEU and HUU and determine associations with neurodevelopmental outcomes.

Aim 2a: To determine the impact of HEU and HUU status, as well as maternal peripartum ART, on neurodevelopment and mental health (ASD, ADHD, depression, and anxiety). We will pilot a mobile screening strategy to detect adverse neurodevelopmental and mental health outcomes in HEU for use in large-scale screening in Aim 2b. Mothers attending HIV care will be invited to bring their HEU (aged 3-18) (200 HEU, 50 per age-stratum: 3-6, 7-10, 11-14, 15-18) for screening; age- matched HUU will be recruited from the community.

Aim 2b. To estimate population-burden and cofactors of adverse neurodevelopmental and mental health outcomes in HEU using mobile teams to screen HEU in ~100 large HIV Care Clinics throughout Kenya (4000 HEU; age-stratified, 3-6, 7-10, 11-14, 15-18) and 400 age-stratum matched community HUU.

Aim 3. To estimate the cost of this screening strategy and convene stakeholders to review data regarding programmatic integration of HEU screening.

12. Study design and methodology

a. Study area description

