For all aims, the study nurse will provide an in-depth explanation of the purpose and procedures of the study, in the language of the woman's choosing, answer any questions the woman may have, and invite the woman to participate in the study. Mothers will be informed that their participation is voluntary and that participation or nonparticipation in the study will in no way alter the nature of health care services that they receive. If interested in participating, the study nurse will screen HEU and HUU mother-infant pairs for eligibility, and, if eligible, woman will provide written consent for enrollment. If the participant is not literate, a witness unrelated to the study will be present and the consent will be read aloud. The participant will provide oral consent with a witnessed thumbprint documented as consent. This system of recruitment has been highly successful in past and ongoing studies conducted by the research team.

HOPE study protocol

Version 1.3

July 21, 2020

Eligibility criteria

Inclusion criteria:

- Infant age 6 weeks (+/- 2 weeks)
- Healthy infant as determined by study nurse
- Mother age ≥ 18
- Planning to remain in study catchment area for 4 years

Exclusion criteria:

- Infant HIV positive
- Mother HIV status unknown (determined using mother-baby maternal and child health booklet)
- Caregiver planning to relocate

iv. Enrollment and study procedures

Data: At enrollment, contact information, maternal sociodemographic characteristics, adverse childhood events (ACEs), depression (maternal PHQ9), obstetric and medical history, and infant birth history and anthropometrics will be assessed. Medical records from MCH/CCC and viral load records will be abstracted from existing data sources. Maternal HIV status will be determined using mother-baby maternal and child health booklet; if the mother has not been tested for HIV, she will be offered HIV testing.

At every visit, study staff will perform anthropometric measurements (height/weight/head circumference, MUAC), neurodevelopmental and mental health assessments, and collect data on past and current child comorbidities and nutrition.

Summary of procedures for recruitment and enrollment

1. MCH nurse reads recruitment script to potential participant
2. MCH nurse refers interested participant
3. MCH nurse documents reason for declining to participate
4. Study nurse assesses eligibility
5. Study nurse gives more information on the study

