Neurodevelopmental assessments: Neurodevelopmental assessments will be conducted by trained study staff to assess developmental progress. The Malawi Developmental Assessment Tool (MDAT) will be used as a measure of infant neurodevelopment. The MDAT assesses gross motor, fine motor, social, and language domains, with 34 pass/fail items in each. Tests will be administered in the preferred language of the child and mother. Scripts for each assessment will be available in English, Kiswahili or Dholuo. Prior to conducting assessments, study staff will undergo several role-playing and practice test sessions, and will have satisfactory performance a monitored practice session. Caregivers will be asked about the child's well-being on the day of testing in order to determine if testing should be rescheduled. During the assessment, children will be given regular breaks as needed. Cognitive skills are assessed within the language and fine motor domains. Most gross and fine motor and language items must be directly observed, and some may be caregiver reported. All social items may be caregiver reported. Items will be administered until a child has 6 consecutive passes and 6 consecutive fails. We will measure interobserver reliability by assessing the same child independently on the same occasion by two observers in a subset.

We will use the Modified Checklist for Autism in Toddlers, Revised and with follow-up (M-CHAT-R/F) to screen for Autism Spectrum Disorders (ASD) at 18 and 24 months of age. Children screening positive will be referred for further assessment and evaluation.

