Child or adolescent age 3-18 years

Child/adolescent is healthy and HIV negative

Mother HIV status known

Mother HIV diagnosis and ART timing known (for HEU)

Caregiver \geq 18 years willing to take children to clinic for evaluation

iv. Enrollment and study procedures

Enrollment will be conducted at a neutral location (typically public MCH clinic) or at home. No additional visits will be conducted after enrollment.

Determination of HIV status for HEU and HUU: A combination of medical records and HIV testing will be used to determine HIV status of mothers and children. Maternal HIV-positive status during the pregnancy with each child will be determined first using the mother-baby maternal and child health booklet; in the event that this

HOPE study protocol

Version 1.3

July 21, 2020

booklet is not available, records from the HIV care clinic documenting the date when the mother was diagnosed with HIV or started ART will be used (only for HIV positive mothers). In the event of no records are available, maternal report of being diagnosed with HIV either during or prior to the pregnancy with each child will be used (only for HIV positive mothers). For mothers who report not being HIV positive at the time of pregnancy and for whom mother-baby maternal and child health booklets are not available, we will offer maternal HIV testing; mothers who do not consent to HIV testing will not be enrolled.

For HEU dyads, children's HIV negative status will be determined using the same set of procedures (first reviewing mother-baby maternal and child health booklet, then infant HIV testing history records); if the child has not been tested for HIV after the cessation of breastfeeding, HIV testing will be offered for the child. Children ages 7-14 years will be asked to provide assent without mention of HIV; children ages 15-18 will be asked to provide assent (or consent for 18 year olds) with explicit mention of HIV testing and will be told that they can choose whether they wish to share their results with their caregivers. If children decline HIV testing, they will not be enrolled in the study.

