For HUU dyads, children will be assumed to be HIV negative if their mother is negative and if they are <15 years of age. Children ages 15-18 will be asked to provide assent (or consent for 18 year olds) with explicit mention of HIV testing and will be told that they can choose whether they wish to share their results with their caregivers. If children decline HIV testing, they will not be enrolled in the study.

At enrollment, growth, neurodevelopmental and mental health outcomes will be collected by interviews with caregivers/adolescents/children. For HIV positive mothers, additional details on HIV treatment history, ART regimen, perinatal illnesses and general health will be obtained from medical records.

Caregivers and adolescents age 18 will give informed consent to participate in the study. Children and adolescents age 7-17 will give assent to participate.

At enrollment, study staff will perform anthropometric measurements (height/weight/head circumference, MUAC), neuro-developmental, mental health and hearing screening and assessments and collect data on past and current child comorbidities and nutrition. Children and adolescents who fail screening tests will be referred for further evaluation as needed.

Summary of procedures for recruitment and enrollment

1. MCH nurse or CHW reads recruitment script to potential participant
2. MCH nurse or CHW refers interested participant
3. MCH nurse or CHW documents reason for declining to participate
4. Study nurse assesses eligibility
5. Study nurse gives more information on the study
6. Interested mothers give informed consent to participate
7. Children age 7 and above give assent to participate
8. Determine maternal and/or child HIV status using medical records
9. Conduct maternal and/or child HIV testing, if not determined using medical records
10. Study staff collect enrollment data - demographics, pregnancy history, ART use and history
11. Study staff conduct anthropometric measures, neurodevelopmental and mental assessments, hearing tests and collect DBS
12. Study staff reimburse client

v. Laboratory methods

HOPE study protocol

Version 1.3

July 21, 2020

Blood samples: Dried blood spots (DBS) for assessment of telomere length will be collected either using finger prick or venous blood draw (0.5ml) at enrollment in 20 selected sites.

HIV testing: HIV testing will be conducted using saliva-based HIV tests, administered by a health care worker.

vi. Data collection instruments

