R33 Aim 2				
Difference in BENC1 scores	0.29	1000 HEU: 100 HUU age stratum (7-11yo)		SD=1.0
Difference in ADHD prev.	7.7%	1000 HEU: 100 HUU		2.7% in HUU ¹⁷⁵
Difference in depression prev	10.1%	1000 HEU: 100 HUU per age stratum		HUU 10%

Analyses: For binary outcomes such as ADHD and depression, multivariate generalized linear models (GLM) with log link and binomial family for relative risk estimation clustered by site will be used. For continuous variables such as NIH-Toolkit, we will use multivariate GLM with Gaussian family and identity link. As previously noted in Aim 1, we will include *a priori* potential confounders - maternal depression, preterm birth, and infant birthweight - in multivariate analysis, after assessment of collinearity.

MDAT (social, fine motor, gross motor, language)	GLM
Hearing	GLM
BENCI (processing speed, visual-motor coordination, attention, language, memory, executive function)	GLM
SDQ total domain score	GLM
ADHD screen (analyze positive SNAP-IV and subset validated on MINI-Kid)	GLM
PHQ-9 (prevalence of moderate-severe symptoms)	GLM
Neuropsychiatric diagnoses	GLM

Training procedures for aim 1 and 2

The study team will develop protocols and training materials for clinic staff. A 5-day training workshop will be designed. The package will include the basics of early childhood development, pediatric mental health, screening and use of the study screening and diagnostic tools. The training will cover neurodevelopmental assessments, psychometric testing, and administration, scoring and interpretation of the MDAT and NIH Toolbox. The 5-day nurse training workshop will cover general sensitization to the testing situation, including ensuring that the child follows the instructions, methods of cross-checking to determine whether a child understood instructions, learning when to give breaks, how to re-engage the child and how to react to distress. The training will cover how to recognize need for referrals and provide motivational interviewing and culturally sensitive assessment skills. To ensure quality control, the study coordinator will conduct refresher training for staff to ensure operating procedures are followed consistently. We will also develop checklists for tests requiring multiple tests as well as the use of tablet based tests to ensure quality assessments.

e. Aim 3

i. **Study design**

This Aim of the study involves 2 cross-sectional components:

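### Aim 2 admits only 'healthy' children, undefined and with no exemption for the conditions under study, so the HEU burden estimate can be biased downward

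*Protocol*

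**What the plan says.** In the Protocol, section 12.d.iii (Aim 2, Eligibility criteria), one condition for HEU and HUU alike is: "Child/adolescent is healthy and HIV negative". No definition, list of conditions or exemption follows. Aim 1 has a parallel criterion in section 12.c.iii: "Healthy infant as determined by study nurse".

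The objectives are population-level. Section 11 gives Aim 2b as "To estimate population-burden and cofactors of adverse neurodevelopmental and mental health outcomes in HEU", and section 10 (Rationale) promises a "national population-based estimate of HEU burden of developmental and mental health outcomes".

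The numbered procedures in section 12.d.iv place the eligibility check at step 4 and the neurodevelopmental, mental health and hearing assessments at step 11. The same section says that staff will "collect data on past and current child comorbidities and nutrition". For binary outcomes, section 12.d.vii plans "multivariate generalized linear models (GLM) with log link and binomial family for relative risk estimation clustered by site". Section 16, on limitations, does not mention the health criterion.

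**The concern.** The Aim 2 outcomes (hearing, ADHD, depression, neuropsychiatric diagnoses, cognitive scores) are themselves states of health. A nurse who takes the criterion at its word may turn away a child with known autism, hearing loss or psychiatric illness, and step 4 comes before step 11, so that child is never measured. The wording would be applied in about 100 clinics, each free to read it differently.

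What is at stake is the burden figure to be shown to policy makers at the Aim 3 workshop. If cases are excluded more often than non-cases, prevalence is too low, and enrolling more children does not repair it. The loss would also go unseen: the procedures record reasons for declining (step 3), but not the health reason for which a child is found ineligible.

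**Working it through.** **The plan's own figures.** The protocol gives no rate of exclusion for ill health. Its nearest figures are the Aim 2 detectable differences in section 12.d.vii, used here as planning values for 1000 HEU and 100 HUU per stratum at 80% power and alpha 0.05 (two-sided assumed).
- ADHD: HUU 2.7%, detectable difference 7.7 points. The difference d solves d = 1.96·√[p̄(1−p̄)(1/100+1/1000)] + 0.842·√[p₁(1−p₁)/100 + p₂(1−p₂)/1000], with p̄ the pooled rate. This gives d = 7.66 points, which reproduces the stated value. The implied HEU rate is 2.7 + 7.7 = 10.4%.
- Depression: HUU 10%, stated difference 10.1 points, implied HEU rate 20.1%. The same formula gives 11.0 points, so 10.1 is not reproduced (power at 10.1 is 73%). It is used below only as a planning value.

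**Effect on burden.** Let p be the true prevalence, s the share of cases turned away and u the share of non-cases turned away. Then

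observed prevalence = p(1−s) / [p(1−s) + (1−p)(1−u)].

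This is below p whenever s > u and equals p when s = u. All values of s and u are assumptions.

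Illustration with assumed prevalence 12% (HEU) and 8% (HUU), and u = 2%:

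| s in both groups | HEU | HUU | HEU burden understated by | Difference (points) | Relative risk |
|---|---|---|---|---|---|
| 2% (= u) | 12.0% | 8.0% | 0% | 4.0 | 1.50 |
| 5% | 11.7% | 7.8% | about 3% | 3.9 | 1.50 |
| 25% | 9.45% | 6.24% | 21% | 3.2 | 1.51 |
| 50% | 6.50% | 4.25% | 46% | 2.3 | 1.53 |

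For example, HEU at s = 25%: 0.12×0.75 = 0.0900; 0.88×0.98 = 0.8624; 0.0900/0.9524 = 9.45%; (12 − 9.45)/12 = 21%.

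On the planning values with u = 0 and s = 50%, HEU depression falls from 20.1% to 0.1005/(0.1005+0.799) = 11.2%, and HEU ADHD from 10.4% to 0.052/(0.052+0.896) = 5.5%.

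**Effect on the contrast, equal exclusion.** The odds in each group are multiplied by the same factor (1−s)/(1−u), so the odds ratio does not change. With the planning values and s = 50%:
- ADHD: the difference falls from 7.7 to 4.1 points; the relative risk goes from 3.85 to 4.01; power falls from 80% to 38%.
- Depression: the difference falls from 10.1 to 5.9 points; the relative risk goes from 2.01 to 2.12; power falls from 73% to 43%.

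The risk difference and the power shrink, while the relative risk that the plan will estimate moves slightly away from 1.

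**Effect on the contrast, unequal exclusion** (depression, u = 0; true difference 10.1 points, relative risk 2.01):
- 50% of HUU and 10% of HEU cases excluded: 18.5% versus 5.3%, difference 13.2 points, relative risk 3.51 (overstated).
- 25% of HUU and 50% of HEU cases excluded: 11.2% versus 7.7%, difference 3.5 points, relative risk 1.45 (understated).

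Section 12.d.iii recruits HEU through HIV clinics and HUU through household visits, so unequal application is possible, but nothing in the protocol says which group would lose more cases.

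**The case against.** The strongest reply is that the protocol nowhere says such children are excluded. It records comorbidities in enrolled children (section 12.d.iv) and takes a mental health history (section 12.d.vi), which suggests that the criterion does not mean free of every condition. Most outcomes are found by screening after eligibility, so undiagnosed cases still enter. This stands, and it limits the loss to conditions already known or visible. It does not tell the nurse at step 4 what to do, and the children most exposed may be the most severely affected.

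A second reply is that the word may mean only fit for testing that day. If exclusion is unrelated to outcome, no estimate is biased. A reader might infer that the criterion serves no such purpose because staff already ask about well-being to "determine if testing should be rescheduled". That sentence stands in the Aim 1 instruments (section 12.c.vi); the Aim 2 text has no such rule, so a same-day fitness check remains a plausible intent there. If that is the intent, the criterion should say so.

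A reader might also infer that the group contrast is pulled toward no difference because HEU have more morbidity. The documents do not support this. The morbidity described in section 8 is largely mortality, pneumonia, diarrhoea and hospitalization, not diagnosed disability at 3 to 18 years, and the calculations above show that the direction is not fixed.

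Finally, a reader might extend the point in full to Aim 1. At 6 weeks the SDQ and autism-screen outcomes and later MDAT change do not yet exist, so a baseline health criterion is mostly not selection on the outcome. The enrolment hearing screen and baseline MDAT are the exceptions. Section 16 already concedes under-ascertainment of perinatal morbidity.

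**Conclusion.** The point holds for the Aim 2 burden estimate. An undefined health requirement, applied before assessment and with no exemption for the outcome conditions, conflicts with a population-burden objective. If it is applied as written to children with known conditions, the HEU prevalence is biased downward.

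The size cannot be determined from the documents. A relative understatement of about 3% to 46% corresponds to 5% to 50% of cases being turned away, under an assumed 12% prevalence and 2% exclusion of unaffected children. It is nil if cases and non-cases are excluded at the same rate. The upper figures should not be read as expected values.

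For the HEU versus HUU contrast the direction of bias is uncertain. Equal exclusion lowers the risk difference and the power but does not attenuate the planned relative risk; unequal exclusion can go either way. For Aim 1 only a clarification is needed.

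**What to change.** In section 12.d.iii, replace the health requirement with absence of acute illness on the assessment day, rescheduling if it is present, and keep the HIV-negative requirement. State that developmental, mental health, hearing and chronic conditions are not grounds for exclusion. Log the health reason for each child not enrolled, so that any remaining selection can be described by group and by site. In section 12.c.iii, state in the same way that a suspected developmental or hearing problem does not make an infant ineligible.

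No scoring rule for children who cannot complete a test is needed for this fix. Assigning them a floor score could misclassify, for example, a motor or visual barrier as a cognitive deficit.

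The cost is a short eligibility amendment with matching edits to the recruitment and screening forms. Rescheduling before enrolment does not conflict with the rule that no visits follow enrolment. A small downside is that a few enrolled children may not complete every instrument.

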Child mental health screening. The SDQ (described above) will be used to screen for mental health conditions in children through age 16 years. In 7-11 year old orphans in South Africa, the Parent SDQ had good construct validity with the Computerized Diagnostic Interview Schedule for Children -4th Ed. (CDISC-IV), with area under the curve (AUC) ranging from 0.73-0.82¹³⁸. In pre-school aged children the Total Difficulties Score (TDS; an aggregate) had 0.79 sensitivity and 0.93 sensitivity versus the Child Behavior Checklist¹⁴⁰. For older adolescents (>16 yrs), the PHQ-9 is a widely used screening test for depression validated in Ethiopia, Nigeria, Kenya and Uganda¹⁴¹⁻¹⁴³. In 15-40 year olds in Nigeria, the PHQ-9 had ≥ 0.85 sensitivity and 0.99 specificity for combined major and minor depressive disorders and major depression¹⁴⁴. We will administer SDQ to the child and with the parent (will respond to questions about their children).

Screening for ADHD. Because the SDQ may not optimally screen for ADHD, the SNAP-IV (revision of the Swanson, Nolan, and Pelham – SNAP) questionnaire will be administered to screen for ADHD^{145,146}. The Multimodal Treatment Study (MTA) version includes 26-items, has robust psychometric properties¹⁴⁵ and a caregiver/parent only approach has been used in South Africa¹⁴⁷. As in this South African study a score at the 95th percentile will be considered positive and will prompt further evaluation with the MINI-KID.

Diagnosis of neuropsychiatric disorders. The Mini International Neuropsychiatric Interview for children and adolescents (MINI-KID)^{148,149} is a diagnostic tool that included diagnosis of over 30 common pediatric psychiatric

HOPE study protocol

Version 1.3

July 21, 2020

morbidities among children and adolescents age 6-17 years, including depressive disorders, suicidality, anxiety disorders and ADHD.¹⁵⁰ The MINI-KID and the corresponding adult form (MINI) will be used to evaluate children and adolescents who screen positive on the SDQ or PHQ-9. Administration can take as little as 10 minutes by nurses and social workers¹⁵¹. The MINI-KID has been used in Nigerian and Ugandan adolescents age 10-19^{152,153}. Diagnosis of major depressive episodes using MINI-KID in Rwanda in 10-17 year olds aligned with local expression of depression-like symptoms¹⁵⁴.

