Cognitive outcomes. Cognitive assessments will be done using NIH Toolbox. The battery will include the tests Dimensional Change Card Sort Test, Flanker Inhibitory Control and Attention Test, List Sorting Working Memory Test, Pattern Comparison Processing Speed Test, and Picture Sequence Memory Test, which evaluate working memory, attention, processing speed, and other aspects of executive functioning. The NIH Toolbox has been validated for US children and was recently adapted through a rigorous process involving translation and backtranslation for Kenya, including translation to Dholuo and Kiswahili.

The table below summarizes the tools, age-group they are used in, screening time and domains or disorders they test.

Tool	Age-group	Time (minutes)	Types	Domains/Disorder
MDAT	0.6-5	30	Screening	Gross motor, fine motor, language, social
HearScreen TM	3+	5	Screening	Hearing
NIH Toolbox	6-17	25-30	Screening	working memory, attention, processing speed, executive functioning
Strengths and difficulties questionnaire (SDQ)	3-16 & caregivers	10	Screening	Emotional symptoms, conduct problems, hyperactivity/inattention, peer relationship problems
SNAP-IV	6-12	5-10	Screening	ADHD
PHQ-9	>16 & caregivers	3	Screening	Depression
MINI-KID	6-17	10	Diagnostic	Common psychiatric conditions
MINI	18	10	Diagnostic	Common psychiatric conditions
School performance	>10	1	NA	National exam results Parental report

vii. Sample size determination & data analysis

Effect size calculations: For comparisons of z-scores in MDAT or NIH-toolkit scores, we will be able to detect differences of 0.13-0.18 assuming a standard deviation of 1.0 or 1.4, 80% power and alpha of 0.05 in Aim 1 cohort (Table 10). In the cross-sectional cohort, 2- to 3-fold differences will be detectable, in diagnoses such as depression and ADHD. To detect smaller differences, more HUU could be enrolled in some age-strata based on pilot feasibility.

R61/R33 Aim 1 cohort	Effect detectable (no attrition)		Effect detectable (20% attrition)	Assumptions
Difference in z-score for MDAT	0.13 (SD=1.0)	1000 HEU:1000 HUU	0.14 (SD=1.0)	Standard deviation = 1.0-1.4 ¹⁰⁵
	0.18 (SD=1.4)		0.20 (SD=1.4)	
Difference in ASD prevalence	2.2%	1000 HEU:1000 HUU	2.5%	HUU ASD 2%
	3.3%	500 DTG: 500 EFZ	3.8%	
Difference in SDQ+ prev.	5.2%	1000 HEU:1000 HUU	5.9%	HUU SDQ+ 20%
	7.5%	500 DTG: 500 EFZ	8.5%	
Difference in hearing loss	1.7%	1000 HEU:1000 HUU	2.0%	HUU 1%
	2.7%	500 DTG: 500 EFZ	3.1%	
Difference in TL	0.18	500 HEU: 500 HUU		SD=1.0

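### At the tabled 1000:100, the Aim 2 ADHD row needs about a 3.9-fold difference, not 2- to 3-fold; the depression row should read 11.0 points, and the cognitive figures carry the wrong labels

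*Protocol*

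**What the plan says.** All of this stands in protocol section 12.d.vii (Aim 2, sample size and data analysis) unless noted.

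- The text on diagnoses reads: "In the cross-sectional cohort, 2- to 3-fold differences will be detectable, in diagnoses such as depression and ADHD".
- The Aim 2 block of the table has a row "Difference in ADHD prev" with 7.7% at 1000 HEU to 100 HUU and 2.7% in HUU.
- The depression row gives 10.1% for "1000 HEU: 100 HUU per age stratum", with 10% in HUU. It names no instrument.
- The text on cognition reads: "For comparisons of z-scores in MDAT or NIH-toolkit scores, we will be able to detect differences of 0.13-0.18". It continues with SD 1.0 or 1.4, "80% power and alpha of 0.05 in Aim 1 cohort (Table 10").
- The only cognitive row for Aim 2 is for BENCI, 0.29 at SD 1.0, "1000 HEU: 100 HUU age stratum (7-11yo").
- The analysis table lists "BENCI (processing speed, visual-motor coordination, attention, language, memory, executive function").

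Section 12.d.vi names NIH Toolbox (five tests, ages 6-17) as the cognitive instrument; its tool table does not contain BENCI. SNAP-IV is for ages 6-12, MINI-KID for 6-17 and MINI for 18. It also says "For older adolescents (>16 yrs), the PHQ-9 is a widely used screening test for depression". The strata are 3-6, 7-10, 11-14 and 15-18 (section 11, Aim 2b). Aim 1 follow-up ends at age 4 (section 12.b).

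**The concern.** The text and the table state different detectable effects for ADHD from the same design, and one tabled figure does not follow from its own inputs. A reader who takes the sentence at face value would believe that a doubling or tripling of ADHD could be found within the tabled groups.

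Section 9 describes the age strata as adequately powered for mental health outcomes, and section 12.d.vii leaves open enrolling more HUU in some strata to detect smaller effects. Both the reading of a null HEU-HUU contrast and that enrolment decision rest on these figures. For cognition, no detectable difference is correctly labelled for the instrument and ages actually planned.

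**Working it through.** **Inputs.** Power 80% and alpha 0.05 are stated for Aim 1. Two-sided testing is my assumption: it reproduces the Aim 1 rows, and I carry it to Aim 2. Group sizes and HUU rates are those in the table.

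**Formula for proportions.** With pooled rate p̄, s0 = √[p̄(1−p̄)(1/n₁+1/n₂)] and s1 = √[p₁(1−p₁)/n₁ + p₂(1−p₂)/n₂]. Power = Φ[(d − 1.960·s0)/s1]. The detectable difference is the d that gives 0.80.

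**Reproducing the plan's rows.** Aim 1, without attrition:

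| Row | 1000:1000, stated / recomputed | 500:500, stated / recomputed |
|---|---|---|
| ASD, HUU 2% | 2.2 / 2.16 | 3.3 / 3.32 |
| SDQ, HUU 20% | 5.2 / 5.24 | 7.5 / 7.53 |
| Hearing, HUU 1% | 1.7 / 1.68 | 2.7 / 2.67 |

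The 20% attrition columns agree to within 0.1 point. For ADHD (100 at 2.7%, 1000 HEU) the formula gives 7.66 against 7.7 stated. So this is the method in use.

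**ADHD as a ratio.** (2.7 + 7.7)/2.7 = 10.4/2.7 = 3.85, about 3.9-fold.

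- 3-fold (2.7% vs 8.1%): p̄ = 0.0761, s0 = 0.0278, s1 = 0.0184. (0.054 − 0.0545)/0.0184 = −0.03, so power is 49%.
- 2-fold (2.7% vs 5.4%): p̄ = 0.0515, s0 = 0.0232, s1 = 0.0177. (0.027 − 0.0455)/0.0177 = −1.04, so power is 15%.

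**Depression.** For 100 at 10% and 1000 HEU the detectable difference is 10.97 points (10% to 21.0%, 2.1-fold), not 10.1. At 10.1 points: p̄ = 0.1918, s0 = 0.0413, s1 = 0.0326; (0.101 − 0.0809)/0.0326 = 0.62, so power is 73% (74% by exact enumeration of the chi-square test). Other methods give 9.1 (unpooled), 10.4 (arcsine), 10.9 (likelihood ratio) and 11.6 (continuity-corrected). One-sided testing with continuity correction comes to 10.08 but does not fit the other rows. The pooled formula returns 10.1 only if the HUU rate is about 7.5%.

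**Ages behind the depression row.** MINI-KID starts at 6 and PHQ-9 applies above 16. Ages 3-5 therefore have no depression diagnostic, and 1000:100 cannot hold in the 3-6 stratum.

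**Cognition.** Detectable difference = 2.802·SD·√(1/n₁+1/n₂).

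- 1000:1000: 0.125 (SD 1.0) and 0.175 (SD 1.4). This matches 0.13-0.18 and is right for MDAT in Aim 1.
- 1000:100: 0.294 (SD 1.0) and 0.411 (SD 1.4). The first matches the tabled 0.29.

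Toolbox starts at 6 and Aim 1 ends at 4, so 0.13-0.18 cannot apply to Toolbox in that cohort. BENCI is not in the battery, and ages 7-11 cut across the 7-10 and 11-14 strata.

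**The case against.** Much of the table is right. The 7.7 and 0.29 both reproduce, and 0.13-0.18 is correct for MDAT, so a reader who infers that the Aim 2 figures are wrong throughout goes too far. For ADHD only the prose summary fails.

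The ADHD row, unlike the other two Aim 2 rows, names no stratum, and the sentence speaks of the whole cross-sectional cohort. Larger groups would bring the ratio into range: about 2.9-fold at 1750:175 and 2.15-fold at 4000:400. That stands as arithmetic. But the table states 1000:100, and SNAP-IV is given only at ages 6-12, so 4000:400 is not available for the ADHD screen. The protocol's remark that more HUU could be enrolled is a possibility, not a commitment, and does not make the sentence true.

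The depression error is small: 10.1 and 11.0 points are both about 2-fold, within the stated range.

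A reader might also infer that the depression row assumes PHQ-9 at ages that never receive it, and so has very low power. The document does not say this. The row names no instrument, the sentence speaks of diagnoses, and MINI-KID and MINI diagnose depression in screen-positives aged 6-18. A 500:50 group for PHQ-9 is an assumption about how ages spread within 15-18, and no detectable difference is stated for PHQ-9 that could be contradicted.

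Finally, Aim 2b is chiefly about burden and cofactors in HEU, which these rows do not govern.

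**Conclusion.** The point holds in limited form and should be fixed.

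- The 2- to 3-fold claim contradicts the ADHD row: at 1000:100 it is about 3.9-fold, with 49% power at 3-fold and 15% at 2-fold.
- The depression figure should be 11.0 points. The stated 10.1 has about 73% power. The fold statement survives for depression.
- The depression row cannot apply to every stratum, because ages 3-5 have no diagnostic tool.
- The cognitive arithmetic is right, but the labels are wrong: NIH Toolbox in the Aim 1 sentence, BENCI in the Aim 2 row and analysis table, and a 7-11 age group that is not a stratum.

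The results assume two-sided 5% testing, 80% power and the tabled rates and group sizes. Neither the protocol's figures nor mine allow for clustering by site, which the analysis does include.

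**What to change.** In section 12.d.vii:

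1. Replace the fold sentence: at 1000:100, about 3.9-fold (7.7 points) is detectable for ADHD and about 2.1-fold (11.0 points) for depression. Optionally add ADHD pooled over SNAP-IV ages 6-12. If ages are evenly spread within strata this is 250 + 1000 + 500 = 1750 HEU and 175 HUU, giving about 5.3 points or 2.9-fold.
2. Correct the depression row to 11.0 points, limit it to strata with a depression diagnostic, and name the instrument.
3. If PHQ-9 is analysed as an outcome in its own right, as the analysis table lists it, give its detectable difference for ages above 16 only, conditional on the number in that range (for example 16.5 points if 500:50).
4. Remove NIH-toolkit from the Aim 1 sentence.
5. Relabel the BENCI row as NIH Toolbox for the actual strata: 0.29 (SD 1.0) to 0.41 (SD 1.4) at 1000:100. Only 7-10 and 11-14 lie wholly within the Toolbox age range.
6. Replace BENCI and its domains in the analysis table with the five Toolbox tests.
7. State that the figures do not allow for clustering by site.

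The cost is a text amendment with less favourable figures and no extra participants.
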